5.5 Eligibility criteria

5.5.1 Inclusion criteria

We will enroll HEU and HUU children from 5 years to 14 years of age from the PROMISE ND study into the present study. The HIV+ children needed for the target enrollment at each of the two sites will be new recruitments carried out in the MUJHU Kampala or JHU Malawi clinical care treatment programs serving children living with HIV. These HIV+ children will be age-matched and gender balanced to the PROMISE ND HEU and HUU cohorts enrolled in the present study. When evaluating BPG neuropsychological outcomes for the HEU and HUU cohorts, we will control for number of prior neuropsychological assessments, since these children will have had three prior assessments with the KABC-II test, and will be more experienced in that regard than the testing-naïve clinic HIV+ children. The PROMISE ND HEU HUU cohorts in the present study will all be equally experienced in terms of prior neuropsychological testing.

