With NIH funding we previously developed BPG (Brain Powered Games), a CCRT (Computerized Cognitive Rehabilitation Therapy) digital games package for HIV+ school children in the sub-Saharan. As a child plays, BPG gathers game data that can be used for neurocognitive assessment. In this new study, we will further evaluate the capability of BPG as a test for neurodevelopment. In a second phase, we will add an award-winning game developed at the MSU-GEL lab that will train executive function (EF), allowing us to dynamically assess this often-neglected neurocognitive domain in previously tested and well-characterized HIV+, HEU and HUU cohorts of children.

In Study Aim 1 we will adapt and evaluate concurrent and predictive validity of BPG. Here we will evaluate whether BPG as a static (baseline) assessment corresponds to a gold standard of static measures (KABC-II,

TOVA, CogState). Compared to these, we hypothesize that dynamic BPG assessments will be feasible and acceptable, providing for a more sensitive evaluation of brain/behavior function as affected by more proximal factors of HIV exposure, disease and treatment. We also hypothesize that dynamic assessments will be more sensitive to distal developmental risk factors (e.g., SES, nutrition/growth, maternal caregiving quality), measured in early childhood in study cohorts.

In Study Aim 2, we will compare the validity of BPG static and dynamic assessments. Here we will validate BPG static and dynamic assessments with a gold standard of neuropsychological tests previously used with school-age children at our two study sites (Kampala, Uganda and Blantyre, Malawi). Cohorts will be well characterized due to participating in our previous NIH-sponsored HIV clinical trials. We hypothesize that BGP-based static and dynamic assessments will be sensitive to cohorts' prior longitudinal trajectories as affected by proximal and distal risk factors that cause developmental delay and cognitive problems, as measured in our previous clinical trial studies with these cohorts. The executive function game will prove especially sensitive.

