5.2 Study goals, aims and objectives

5.2.1 Study Goal

The overall goal of this research is to adapt and validate BPG as a measure to assess cognitive changes as a child plays with BPG once (static assessment) and over the course of 12 training sessions (dynamic assessments of cognitive change over time).

5.2.2 Aims and objectives:

Aim 1: To adapt and evaluate concurrent and predictive validity of BPG static (baseline) and dynamic (during 12 training sessions) cognitive assessments at the Malawi and Uganda sites.

Objective 1.1 To evaluate whether BPG static (baseline) assessment corresponds to the gold standard static measures previously adapted to HEU, HUU, and HIV+ study cohorts at Uganda and Malawi country sites (KABC-II, TOVA, CogState).

Aim 2: To compare the validity of BPG static and dynamic assessments.

Objective 2.1 To evaluate the correspondence of BGP-based static and dynamic assessments the cohorts' prior early childhood longitudinal trajectories (KABC-II), considering the effect of proximal (e.g. HIV status) & distal (height, weight, HIV disease factors, demographic) risk factors causing developmental delay and cognitive problems.

Aim 3: To test the sensitivity of dynamic assessment to learning loss over time by evaluating how much BPG performance gains diminish during a 6-month absence of training

Objective 3.1 To assess change over time in KABC-II, TOVA and CogState scores (learning loss) 6 months after the children complete 12 sessions of BPG training, overall and by cohort.

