7.1.2 Statistical Approach by Specific Aim

Statistical analysis for Aims 1& 2. So as not to have to rely on American norms for standardizing our gold standard measures, we will use a statistical technique for standardization described from our cerebral malaria longitudinal studies with these tests.⁶⁵ [name] will evaluate the concurrent validity by computing correlation coefficients of the BPG and “gold standard” measures at intake (see Table 3) at 1 and 7 months. Correlations will be classified as: very strong ($r \geq 0.8$), strong (r range 0.6-0.79), moderate (r range, 0.4-0.59), weak (r range, 0.20-0.39), and very weak (range: 0-0.19). We will summarize the sensitivity of the BPG-based vs gold standard measures to the proximal (HIV infection) and distal factors (SES, home environment, growth) using: 1) relative validity coefficient; 2) standardized effect size;⁶⁶⁻⁶⁹ 3) standardized response mean (SRM) and Guyatt’s SRM.^{66,67,69,70} Larger values of these summary statistics correspond to greater sensitivity or ability to discriminate known groups. Interpretations similar to Cohen’s effect sizes⁶⁸ will be considered (e.g. SRM: ≥ 1.0 : excellent; 0.80-0.99: good; 0.50-0.79: moderate; and < 0.5 : weak). We will evaluate the predictive validity of the BPG-derived measures in the LME model with the repeated gold standard measures at 1 and 7 months (6-month follow-up). Covariates will include the BPG static measure at intake (baseline) and 1 month (post-training BPG; time-varying covariate), time (1 and 7 months), other covariates (proximal and distal factors, Figure 1), and number of prior neuropsychological testing sessions.

Statistical analysis for Aim 3. Two sets of the LME models will be fit: one with 3 repeated “gold standard” measures, and one with 3 BPG-derived measures. To model potential non-linear patterns over time, we will enter time as a class variable with levels of intake, 1, and 7 months. Based on past experience, we expect gains in outcomes between intake and 1 month due to training, and a slower rate of change in the subsequent 6-month period with no training. Summary statistics for change over time for the gold standard vs BPG-derived measures will be compared as described under statistical analysis for Aim 1.

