Sample sizes for Aims 1, 2, and 3. Sample size considerations are based on having sufficient power to discriminate known groups based on the proximal factor of HIV status/exposure, a key factor for Aim 1. The preliminary data from PROMISE ND study indicate that the differences in the composite neurodevelopmental score (the Mullen Scale of Early Learning) between HEU and HUU cohorts corresponded to the effect size of Cohen's $d=0.26$ (difference between the means of 0.26 of the standard deviation). To detect this difference between HUU and HEU cohorts, $n=240$ per cohort is needed for power ≥ 0.80 in two-tailed tests at 0.05 level of significance. Based on the preliminary data, the effect size d for comparisons of the HIV vs HUU or HEU is at least 0.31. This can be detected with power ≥ 0.80 with $n=120$ in the HIV group. Therefore, the proposed total sample size for both sites combined is $n=240$ HUU; $n=240$ HEU; and $n=120$ for HIV+ children.

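### If HIV+ children are recruited untested from clinics, the prior-test covariate cannot separate test experience from HIV infection

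*Combined protocol and SAP*

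**What the plan says.** Section 5.5.1 makes three statements that matter here.

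- On the HEU and HUU children: "we will control for number of prior neuropsychological assessments, since these children will have had three prior assessments with the KABC-II test". It adds: "The PROMISE ND HEU HUU cohorts in the present study will all be equally experienced in terms of prior neuropsychological testing".
- On the HIV+ children: "The HIV+ children needed for the target enrollment at each of the two sites will be new recruitments carried out in the MUJHU Kampala" or the Malawi care programmes. The section treats these children as having no test experience.
- It gives this difference in experience as the reason for the control.

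Section 7.1.2 describes one model that uses the count: "We will evaluate the predictive validity of the BPG-derived measures in the LME model with the repeated gold standard measures" at 1 and 7 months. Beside the BPG terms and time, its covariates are "other covariates (proximal and distal factors, Figure 1), and number of prior neuropsychological testing sessions". Figure 1 was not available to me, but the text makes HIV status a proximal factor. Section 7.1.2 names HIV infection in that role, Objective 2.1 in Section 5.2.2 speaks of "considering the effect of proximal (e.g. HIV status" and the like, and the sample-size paragraph refers to "sufficient power to discriminate known groups based on the proximal factor of HIV status/exposure".

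The documents disagree on two facts that decide how the count behaves.

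- **Prior KABC-II assessments.** Section 5.5.1 says three. Section 5.4 lists KABC-II at two ages (48 and 54 to 60 months).
- **Source of the HIV+ children.** Section 5.5.1 says new clinic recruits, and Section 5.4 makes P1104s graduates a fallback. Section 8.1 lists P1104s without condition. Sections 2.0 and 4.0 describe the HIV cohort as the P1104s cohort, and Section 3.0 speaks of "previously tested and well-characterized HIV+, HEU and HUU cohorts of children".

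**The concern.** A covariate can adjust a group contrast only if it varies within the groups. On the Section 5.5.1 values it does not: every HEU and HUU child has the same count and every HIV+ child has zero. The plan then presents the cohort difference in test experience as controlled when the design cannot control it.

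At stake is the reading of any HIV+ versus HEU or HUU contrast. If practice on the KABC-II helps, part of an apparent HIV+ deficit on that test could be lack of practice. The known-groups comparison of KABC-II with BPG carries the same confounding with prior KABC-II experience, although it is not fitted with this covariate.

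**Working it through.** **Inputs.** Cohorts of 240 HUU, 240 HEU and 120 HIV+ (Section 7.1.2). A common prior count k for HEU and HUU, with k = 3 from Section 5.5.1 or k = 2 from the ages in Section 5.4. Count 0 for clinic-recruited HIV+ children (Section 5.5.1).

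**The plan's own figures.** The plan gives no figure for this adjustment. Its sample sizes are not in dispute. For d = 0.26 the normal approximation needs 233 per group, and 240 gives power 0.81. For d = 0.31 with 120 against 240, power is 0.79, close to the stated 0.80. These are unadjusted two-group calculations and do not involve the count.

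**Aliasing.** Let H = 1 for HIV+ and 0 otherwise. Then count = k − kH, and

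βH + γ × count = kγ + (β − kγ)H.

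Only β − kγ can be estimated, never β (HIV+) and γ (per test) separately. With columns intercept, HEU, HIV+ and count over 600 children, the rank is 3 of 4 for any common k. With two rows per child and time added it is 4 of 5. A fuller design (time, two BPG terms and one distal covariate added) has rank 7 of 8, also if the count rises by one at each study visit.

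**The other two readings.**

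- HEU and HUU only: the count is a constant, and intercept, HEU and count have rank 2 of 3.
- HIV status left out: the count is a rescaled HIV+ indicator. In simulated data with k = 3, an HIV+ difference of −0.300 reappears as a count coefficient of 0.100 = 0.300/3.

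**What is not touched.** In the same simulated data the BPG coefficient (0.222) and the HEU coefficient (−0.243) are identical with and without the count.

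**If the tie is broken.** The documents give no such counts, so these are assumptions. Without the count, the variance of the HIV+ versus HUU coefficient is proportional to 1/120 + 1/240 = 0.0125. With it,

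inflation = 1 + D² / (0.0125 × S),

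where D is the difference in mean count between HIV+ and HUU and S is the within-cohort sum of squares of the count. If m of 120 HIV+ children have the same count as HEU and HUU, this reduces to 1 + (120 − m)/(1.5m).

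| m | Same count | HIV+ count 2, HEU/HUU 3 | HIV+ count 3, HEU/HUU 2 |
|---|---|---|---|
| 6 | 1 + 114/9 = 13.7 | 30.5 | 6.3 |
| 12 | 1 + 108/18 = 7.0 | 15.5 | 3.4 |
| 30 | 1 + 90/45 = 3.0 | 6.6 | 1.6 |
| 60 | 1 + 60/90 = 1.7 | 3.7 | 1.1 |

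Section 5.4 also allows HEU and HUU replacements from other study rosters. With 10 untested replacements split equally, inflation is 1 + (235/240)/0.125 = 8.8. With 24 it is 1 + (228/240)/0.30 = 4.2.

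**The case against.** The strongest reply is that no planned result depends on this. The model's target is BPG, HIV status is only an adjuster, and no section commits to reporting its HIV+ coefficient. Discrimination by HIV status is summarised by other statistics. With HIV status in the model, the experience difference between cohorts is already absorbed and the BPG coefficient is the same either way. Within HEU and HUU alone, a constant count means there is nothing to adjust. If software drops the count as the aliased term, the HIV+ coefficient does not change.

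All of that stands, and it limits the point. A reader might infer that the mixed model or the validity analysis as a whole fails; the documents do not support that. What remains is that Section 5.5.1 promises a control that the design cannot give. A fit may also drop the HIV+ term instead of the count, or return an inflated HIV+ coefficient if a few children break the tie.

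Two further inferences are tempting and should not be drawn.

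- *That HEU and HUU children had seen the KABC-II but not TOVA or CogState.* Section 5.4 is silent on those tests, but Section 2.0 says the evaluative model containing them was also used with the PROMISE ND cohorts.
- *That the practice effect is large.* The documents give no size, and it may have faded. At the Year 1 mean ages in Section 5.4, the gap since the last listed KABC-II is 6.2 × 12 − 60 = 14.4 to 6.6 × 12 − 54 = 25.2 months, and Section 9.0 places enrolment in Years 2 and 3.

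**Conclusion.** The point holds in a bounded form. On the Section 5.5.1 clinic route, the prior-test covariate is an exact function of HIV+ status for any common HEU/HUU count, and the promised control cannot separate test experience from HIV infection. This rests on the nominal counts and on HIV status being one of the proximal factors; if it is not in the model, the count stands in for it.

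The exact tie also depends on where the HIV+ children come from. If half came from P1104s, the inflation would be modest (1.1 to 3.7 over the assumed counts). If only a few did, the HIV+ coefficient would be estimable but imprecise. The BPG coefficients, HEU versus HUU, the primary correlations and the stated power are unaffected. The size of the confounding in HIV+ contrasts is unknown.

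**What to change.** 1. Do not include the prior-test count in any model from which an HIV+ versus HEU or HUU contrast is reported.
2. Replace the claim of control in Section 5.5.1 with a statement that, on the clinic route, these contrasts, including the known-groups comparison of KABC-II with BPG, are confounded with prior KABC-II experience to an unknown degree.
3. Give a count-adjusted contrast only as a sensitivity analysis, if enough previously tested HIV+ children enrol. State the minimum number beforehand; the table above can guide it. The count would then also mark P1104s membership.
4. Say nothing about prior TOVA or CogState exposure unless it is checked against PROMISE ND records.
5. Reconcile the prior KABC-II count (Sections 5.4 and 5.5.1) and the HIV+ source (Sections 2.0, 3.0, 4.0, 5.4, 5.5.1 and 8.1), since these decide whether the tie is exact.

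The cost is one covariate removed from the HIV+ contrasts, one limitation statement and one conditional sensitivity analysis. No new study data are needed. The drawback is that the HIV+ contrast is openly reported as not adjusted for test experience.

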5.5.2 Exclusion Criteria

At pre-BPG study medical examination we will exclude children with a medical history of serious birth complications, severe malnutrition, bacterial meningitis, encephalitis, cerebral malaria, or other known brain injury or disorder requiring hospitalization. Also, children with seizure or other neurological disability will be excluded. This will be screened with P1104s medical history questionnaires. Serious CNS neurodisabilities would prevent such children from completing the BPG intervention, and possibly significant portions of the neuropsychological test battery serving as the evaluative gold standard for static and dynamic assessment outcomes.

5.6 Study Procedures

Study staff will inform PROMISE clinic staff about the Culture-specific neurodevelopment assessment of HIV-affected children Study. After all regulatory approvals are in place and staff trainings have been done, the Culture-specific neurodevelopment assessment of HIV-affected children study staff will receive referrals and recruit interested PROMISE participants into the Culture-specific neurodevelopment assessment of HIV-affected children study. They will then screen and enroll interested PROMISE children at the Kampala and Blantyre PROMISE sites.

To recruit the HIV-infected cohort from the Pediatric HIV Care Center, the Malawi site will first approach the Blantyre District Health Officer for endorsement of the study. Community Educators will then visit health centers to map out their pediatric ART clinic hours, their case load of children living with HIV on ART, general staffing structure and competing research efforts at the clinic that could affect recruitment for the BPG validation study. The Community and Study Clinic departments will follow the proper channels to request permission to give waiting room talks to the children and their caregivers during the pediatric ART clinics and will provide small tokens (pens, etc.) as a reminder about the study to the parents and children approached.

Staff will be positioned at the clinic to meet with patients interested in learning more about the study. When study staff are not present, local health center staff will be asked to call the JHP study clinic anytime a potential participant expresses interest. Recruitment and enrollment will take place at the main study clinic located at the Queen Elizabeth Central Hospital. We will begin by targeting the health centers closer to Blantyre, as persons from these areas have better retention and they are easier to trace in case of a missed visit. We anticipate no challenges in achieving the target 60 HIV-infected children using this approach.

To recruit the HIV-infected cohort (n=60), the Uganda site will approach HIV-infected children from the Pediatric HIV Care Center and Young Generation Alive psychosocial support group, which are affiliated with MUJHU clinical trials unit. Hundreds of children are medically served at the HIV Care Center, most living with HIV. We anticipate no challenges in achieving the target 60 HIV-infected children. Staff will invite to the clinic to

meet with patients interested in learning more about the study. Recruitment and enrollment will take place at the main study clinic located at the MUJHU clinic in Kampala.

To accommodate school-age children's schedules, the site proposes to conduct most study visits during afternoons, weekends and schools' holidays/breaks. To maximize retention, we will ask caregivers whether they prefer to bring the child to the clinic for testing visits or if there is a safe space near their home or school where they are comfortable conducting the tablet-based trainings with BPG and/or Village Builder for about one hour. We anticipate mothers will be interested in conducting training sessions closer to home, especially given the schedule of Brain Powered Games (BPG) expected to be 2-3 training sessions per week for a total of 12 sessions; however, some might have significant concerns about disclosure of HIV status or study participation if sessions are conducted outside of the study clinic, which is why we will offer different options for training site. We will offer to conduct partner information sessions so that husbands and children's fathers learn of the child's study participation in a transparent, open manner, rather than inadvertent disclosure, which can then lead to premature discontinuation from the study.

Written consent will be obtained from interested participants after explanation of the study and opportunity given to them to ask questions of the study staff. Only after obtaining written informed consent will any study procedures be undertaken for the Culture-specific neurodevelopment assessment of HIV-affected children study visits as described below. For participants who do not meet the eligibility criteria, screening will be once in eligibility is determined.

Consented enrolled Culture-specific neurodevelopment assessment of HIV-affected children study participants will have enrollment and follow-up evaluations related to BPG assessments of neurodevelopment over a 7-months period as outlined below and detailed in the Schedule of Evaluation (SoE)s—see Appendices 1-2.

5.6.1 Randomization procedure

Systematic randomization will be used to assign children within each HIV exposure cohort into BPG training or wait-list conditions. Lists of all children within each cohort will be generated and a simple random sampling will be used to assign children into treatment groups. The first child will be assigned to BPG and the next to wait list. For the HEU and HUU cohorts, separately, two sets of random numbers ranging from 001 to 120 will be generated, and the first 60 random numbers drawn from each set will be assigned to start BPG. The second 60 numbers from HEU and 60 from HUU drawn will be assigned to the wait list condition.

A third set of random numbers ranging from 01 to 60 will be generated for the HIV+ group, the first 30 numbers drawn will be assigned to the BPG group. The second 30 numbers drawn from the HIV+ cohort will be assigned to the wait list condition.

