Study Population: A total of 240 HIV-exposed but uninfected (HEU) and 240 HIV un-exposed uninfected Malawian and Ugandan infants and their caregivers recruited in the Promoting Maternal and Infant Survival Everywhere Neurodevelopmental follow-up study (PROMISE ND) sites at Malawi College of Medicine-Johns Hopkins University (MCM-JHU), Blantyre, Malawi; and at Makerere University–Johns Hopkins University (MU-JHU), Kampala, Uganda respectively. In addition, 120 HIV infected (HIV+) children and their caregivers will be recruited from affiliated health clinics at both Malawi and Uganda sites.

Sample size: A total sample size of 600 children and their caregivers in two study sites (n=300 per site) will be included in this study

Study duration: Approximately 5 years.

Overall goal: This research will adapt and validate BPG as a measure of cognitive performance in school-age children as both a static (1 session of BPG) and dynamic assessment (12 training sessions of BPG)

Aims and objectives:

Aim1: To adapt and evaluate the concurrent and predictive validity of BPG as a static (baseline) and dynamic (during 12 training sessions) cognitive assessment at the Malawi and Uganda sites.

Objective 1.1 To evaluate whether BPG static (baseline) assessment corresponds to the gold standard static measures previously adapted to HEU, HUU, and HIV+ study cohorts at Uganda and Malawi country sites (KABC-II, TOVA, CogState).

Aim2: To compare the validity of BPG static and dynamic assessments.

Objective 2.1 To evaluate the correspondence of BGP-based static and dynamic assessments of the cohorts' prior early childhood longitudinal trajectories (KABC-II), considering the effect of proximal (e.g. HIV status) & distal (height, weight, HIV disease factors, demographic) risk factors causing developmental delay and cognitive problems.

Aim3: To test the sensitivity of dynamic assessment to learning loss over time by evaluating how much BPG performance gains diminish during a 6-month absence of training

Objective 3.1 To assess change over time in KABC-II, TOVA and CogState scores (learning loss) 6 months after the children complete 12 sessions of BPG training, overall and by cohort.

Study Outcomes:

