5.0 NEURODEVELOPMENTAL ASSESSMENT PROTOCOL DESIGN

5.1 Overview of Study Design:

[figure not shown]
Static and Dynamic Assessment Process for Each Study Child. Figure 6 provides an overview of study visits and assessments. Following enrollment and physical and medical exams, each child will return to the clinic with their principal caregiver for a half-day of gold standard neuropsychological assessments (KABC-II, TOVA, CogState). At this time the caregiver will complete the Achenbach CBCL questionnaire for school-age children, the Caldwell HOME scale, the SES material possessions evaluation, and the Hopkins Symptom Checklist-25 (caregiver psychological well-being). We will explain assessments and provide instructions in the local language. Study assessments will proceed in two phases. In Phase I, children will be randomized to start BPG trainings (50% of sample) or to a wait-list condition. Within a week after baseline assessment, the full sample of children will be contacted by a field research assistant and facilitate a first BPG session. This first session will be completed by the full sample because it will be considered as an internal performance evaluation session with BPG and will be completed on a tablet, supervised by the field research assistant. This will be done as part of the 50-60 minutes training session on the 5 BPG games (about 10 minutes per game), and will constitute the BPG static assessment. Thereafter, the field research assistant will return with children allocated to the BPG trainings (50% of sample) at a convenient time and supervise BPG training several times per week until 12 training sessions are completed. The 12th session internal evaluation performance measures for the 5 core games and one added EF game will provide the endpoint for BPG dynamic assessment (gain in BPG performance from session 1 to session 12). Because BPG training will occur on a tablet connected to the internet through the mobile network, performance data can be uploaded for analysis via the MSU GEL lab principal server, as done in the Kayunga Uganda CCRT study with BPG ¹.

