5.4 Recruitment

Six hundred African children will be recruited into this study at Clinical Research Sites in Kampala, Uganda and Blantyre, Malawi (n=300/site). These will include 120 HIV infected children from affiliated clinics serving children living with HIV; 240 HEU children from PROMISE study, and 240 HUU children from PROMISE ND study of

similar age group. We will enroll roughly equal numbers of boys and girls, but will not be powered to detect statistically significant differences between them.

Enrollment for the HEU and HUU Cohort

All HIV-exposed but uninfected (HEU) children from the Promoting Maternal and Infant Survival Everywhere Neurodevelopment follow-up (PROMISE ND R01 study) in Blantyre, Malawi (N=188) and Kampala, Uganda (N=208) study sites will be eligible for enrollment for our study since during Year 1 they will be 5 years and older (mean age at both sites 6.6 years, range 5.4-7.7 years). Our target enrollment for this proposal of 120 HEU children from each site (total HEU sample of n=240) during the study's first 2 years that can be easily obtained as it represents 60% of the HEU PROMISE ND cohort at both sites. Our HUU cohort will also consist of 120 HUU children at each study site (total HUU sample of n=240) and will also be recruited from the PROMISE ND cohort study, comprised of 178 HUU children in Malawi and 195 in Uganda. Our target enrollment of HUU children of 120 at each of these two sites is feasible given that it represents 64% of the PROMISE ND cohort and children will be within the required age range (mean age at both sites 6.2 years, range 4.9-7.4 years). In total, 240 HEU and 240 HUU children will be enrolled for the present study.

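### Section 5.6.1 gives allocation rules that cannot all be followed; one of them, alternation, could make assignment predictable and bias any trained versus wait-list comparison

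*Combined protocol and SAP*

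**What the plan says.** Section 5.1 sets a 1:1 split: "In Phase I, children will be randomized to start BPG trainings (50% of sample) or to a wait-list condition". Section 5.6.1 is meant to say how the split is made. It gives four statements in turn:

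- a label: "Systematic randomization will be used to assign children within each HIV exposure cohort into BPG training or wait-list conditions"
- simple random sampling from lists: "Lists of all children within each cohort will be generated and a simple random sampling will be used to assign children into treatment groups"
- alternation: "The first child will be assigned to BPG and the next to wait list"
- a draw of numbers. For HEU and HUU, with numbers 001 to 120 in each set, "the first 60 random numbers drawn from each set will be assigned to start BPG" and the second 60 go to wait list. For the third cohort, "A third set of random numbers ranging from 01 to 60 will be generated for the HIV+ group, the first 30 numbers drawn will be" given BPG and the second 30 go to wait list.

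Nothing in the section ranks these statements. It does not name who generates or holds the sequence, how upcoming assignments are concealed, or when a child is assigned relative to consent and baseline testing. It also does not say that the draw is made separately at each site.

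**The concern.** Alternation is not randomisation. Once one assignment is known the rest follow, and here the protocol prints the first one. Under the timeline in Section 9.0, enrolment runs for six quarters (Year 2 Q1 to Year 3 Q2) and BPG training starts in Year 2 Q2, so early children are in training while later ones are still being recruited. Staff who recruit can therefore see past assignments.

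They would also have a practical reason to act on them. Section 5.6 asks for 2 to 3 supervised sessions per week in the trained arm, and says Malawi recruitment begins with nearby health centres because those families are retained and traced more easily. Placing the easier families in the trained arm would be a natural temptation.

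The first BPG session, which is the static measure, is also exposed. Section 5.1 has the field research assistant who supervises it return to train the BPG arm. The intake table in Section 5.6.6 describes that session differently by arm, so the arm may be known before the static measure is taken.

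At stake is the use of the wait-list group to separate training from retest practice. All children repeat the gold-standard tests, so only a soundly allocated untrained group can make that separation.

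**Working it through.** **1. The plan's own split.** Section 5.6.1 sends 60 HEU + 60 HUU + 30 HIV+ = 150 children to BPG. Against 300 per site, 150/300 = 50%, which reproduces Section 5.1. The allocation ratio is not in dispute.

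**2. Are the two rules the same procedure in different words?** Take one drawn order of 120 positions. Alternation gives BPG to the odd positions; the draw gives BPG to positions 1 to 60. They agree on the odd positions in 1 to 60 (30 children) and the even positions in 61 to 120 (30 children), so 60 of 120. For 60 HIV+ children the count is 15 + 15 = 30 of 60. This is chance-level agreement, so two sites could each follow the text and allocate differently.

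**3. Predictability.** Under alternation in enrolment or known list order, correct guesses are 600 of 600.

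Under the draw, suppose the guesser sees all past assignments and always names the arm with more places left. For one block of 2m children with m per arm, the expected number of correct guesses is m + ½[2^(2m)/C(2m, m) − 1].

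- m = 60: 66.38 of 120 = 55.3%
- m = 30: 34.37 of 60 = 57.3%
- Both sites: 2 × (2 × 66.38 + 34.37) = 334.3 of 600 = 55.7%

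Under full concealment it is 300 of 600 = 50%.

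**4. What predictability could do to an arm comparison.** The documents give no figure for steering, so this step is illustrative. In the Blackwell-Hodges model, staff choose a child whose expected outcome is η SD above average when they expect BPG, and η SD below when they expect wait list. With c correct guesses out of 600 and 300 per arm:

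- spurious difference = 2η(c − 300)/300
- standard error = √(2/300) = 0.0816 SD
- type I error from the normal approximation, two-sided 0.05, true effect zero

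| η (assumed) | Alternation: bias (SD), type I | Draw, past seen: bias (SD), type I | Concealed: type I |
|---|---|---|---|
| 0.05 | 0.10, 0.23 | 0.01, 0.052 | 0.05 |
| 0.10 | 0.20, 0.69 | 0.02, 0.059 | 0.05 |
| 0.20 | 0.40, 1.00 | 0.05, 0.087 | 0.05 |

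For example, alternation with η = 0.05 gives 2 × 0.05 × 300/300 = 0.10 SD. That is 0.10/0.0816 = 1.22 standard errors.

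**5. Which analyses use the arm?** The primary outcome (Section 5.3) is a set of correlations between BPG and gold-standard scores. The sample size (Section 7.1.2) rests on differences between HIV-status groups. The Section 7 models list BPG measures, time, proximal and distal factors and prior testing; none has an arm term.

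**The case against.** The best defence is that the alternation sentence is loose wording. It sits between a sentence on simple random sampling and the only operational detail, the draws of 120 and 60. If first and next refer to the order of drawing, alternation along a randomly drawn order is still random and cannot be predicted from enrolment order. That stands as far as it goes: full predictability requires alternation in enrolment or known list order, which Section 5.6.1 permits but does not state. It does not remove the contradiction, because step 2 shows that the two rules still give different assignments along one drawn order.

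A second objection is that no planned analysis compares the arms. That is correct and limits the point. A reader might infer that the primary validity results or the power calculation are undermined; step 5 shows that the documents do not support this. A reader might also take the Aim 3 remark about gains from training as a planned randomised estimate. In context it is an expectation about change over time, offered as a reason to treat time as a class variable.

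Three other tempting readings also fail.

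- **That half the children have no list.** The numbers in 5.6.1 sum to 120 + 120 + 60 = 300, while the plan has 600 ("A total sample size of 600 children and their caregivers in two study sites (n=300 per site) will be included in this study"). But the ranges match the per-site targets: Section 5.4 has "120 HEU children from each site (total HEU sample of n=240") and likewise for HUU, and Section 5.6 has 60 HIV+ per site. The draw was almost certainly meant per site; only those words are missing.
- **That rolling enrolment makes the draw unworkable.** Position numbers can be drawn in advance and matched to children as they enrol.
- **That varying block sizes are needed.** They are a preference; concealment is what matters.

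**Conclusion.** The concern holds as a contradiction in the current text with a bounded consequence. Section 5.6.1 cannot be carried out as written, and one of its rules would make assignment predictable: 100% if alternation follows enrolment or known list order, about 56% under the draw when all past assignments are visible, and 50% under full concealment. All 600 assignments is the ceiling, reached only on the first of these.

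The exposure is selection bias in any trained versus wait-list comparison of gains. Its size depends on an assumed amount of steering. At 0.05 to 0.20 SD, alternation gives a spurious difference of 0.10 to 0.40 SD, against 0.01 to 0.05 SD under the draw. The primary correlations and the stated power are not directly affected, and Section 7 as written tests no arm difference. The text still needs correcting, because a faulty allocation cannot be repaired after enrolment and the wait-list group would be the natural comparator for any claim about training.

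**What to change.** In Section 5.6.1:

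1. Delete the alternation sentence and the word systematic.
2. Keep one random 1:1 procedure, stated as done separately by site and cohort: six lists, with 120 HEU, 120 HUU and 60 HIV+ at each site. The existing number draw will serve; randomly varying block sizes are optional.
3. State that the sequence is generated and held by someone not involved in enrolment or testing.
4. State that each child's arm is released only after consent, the intake gold-standard battery and the first BPG session. Section 5.1 already has every child complete both, so the schedule does not change.

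If an arm comparison is later added to Section 7, include site and cohort as strata.

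The cost is a paragraph of protocol text, the generated lists and a small operational step for concealed release. No extra children or visits are needed.
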